## **11.3 Description of the Analyses**

The TV positive rate will be compared between the two arms for superiority. Additional analyses will be conducted to compare the rates stratified by BV status.

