## 11.7 Sample Size

### Considerations

[figure not shown]
This RCT will allow for evaluation of index dosing of MTZ by BV status. This study examines two hypotheses simultaneously:

H1: Women receiving multi-day MTZ will be less likely to test TV positive at TOC compared to women who receive the single dose MTZ.

H2: This effect (H1) will only be observed among women who have BV (Nugent score  $\geq 7$ ).

From our pilot work, we found the rates of repeat infection at TOC to be 16.2% for single dose and 10.7% for multi dose at a power of 0.80, we will need 1206 subjects. If we account for a 5% Inner Class Correlation (ICC) for correlation of the subjects within the 4 sites using the formula  $1=(M-1)*ICC$ . We will need to inflate by 15%. We will also inflate by 20% to accommodate for our anticipated follow-up for a required sample size of 1664. We will have 1332 evaluable unites at TOC, which will provide adequate power taking into consideration the ICC.

Figure 1.  
Randomization Scheme

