### **11.13 Final Analysis Plan**

Analyses will be conducted in an intent-to-treat manner with variables categorized per protocol. To assure that randomization has been achieved, selected demographic, clinical and behavioral (including medication adherence and sexual re-exposure) factors will be compared by study arms using chi-square, t-test or ANOVA, where applicable. If randomization was found to be successful (as indicated by even distribution of potential confounders) then analyses will be conducted with no need to adjust for confounding. If randomization was not achieved, then associations will be explored for potential confounding and if found these factors will also be included in the model. From the two aims, there are two hypotheses:

H1: Women receiving multi-day MTZ will be less likely to test TV positive at TOC compared to women who receive the single dose MTZ.

H2: This effect (H1) will only be observed among women who have BV (Nugent score  $\geq 7$ ).

Analysis: The research questions will be answered using a multivariable logistic regression analysis to examine the effect of single versus multi-dose (H1) and the differential impact of BV on this effect (H2). This primary logistic model contains two main effects (i.e. treatment and BV)

Version: 11.0

[figure not shown]
Version date: 1/2/17

and 1 first order interaction (BV by index treatment)). The model (1) will be:  $g(Y_i) = \beta_0 + \beta_1 + \beta_2 + \beta_1 \cdot \beta_2$  where:  $g(Y_i) = \log$  odds of repeat infection,  $\beta_0 =$  coefficient for the intercept,  $\beta_1 =$  (Factor 1) single versus multi-dose,  $\beta_2 =$  (Factor 2) BV at time of visit

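### Section 11.13 assigns H1 to a primary model that always contains arm-by-BV and names no H1 contrast, so its treatment coefficient is in general not the overall arm comparison described in 11.3 and used for sizing in 11.7

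*Combined protocol and SAP*

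**What the plan says.** Section 11.3 describes an overall comparison: "The TV positive rate will be compared between the two arms for superiority". It puts the BV-specific results second: "Additional analyses will be conducted to compare the rates stratified by BV status". Section 11.7 sizes the trial on overall rates: "16.2% for single dose and 10.7% for multi dose at a power of 0.80, we will need 1206 subjects".

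Section 11.13 then assigns both hypotheses to one regression: "The research questions will be answered using a multivariable logistic regression analysis to examine the effect of single versus multi-dose (H1") and the differential effect of BV (H2). It goes on: "This primary logistic model contains two main effects (i.e. treatment and BV") "and 1 first order interaction (BV by index treatment"). The interaction is in the model without condition. The equation is written in coefficients only, with no covariates, so the parametrisation cannot be recovered from it. The BV term is defined as ("Factor 2) BV at time of visit". The cut-point for BV, a Nugent score of 7 or more, is defined in 11.5 and in H2. The numerical coding, the reference level and the visit are not given.

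Later in 11.13, a rule says that an interaction that was not expected, with p below 0.10, leads to stratification on BV status.

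**The concern.** Once an arm-by-BV term is in a logistic model, the treatment coefficient is the arm effect at whatever BV value is coded zero. An analyst who follows 11.13 and reads H1 from that coefficient is testing a conditional effect, chosen by a coding decision that the plan does not make. The sample size and 11.3 concern a different quantity, the overall difference between arms. Section 11.13 does not refer back to 11.3 or carry its comparison forward.

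At stake is the answer to the first hypothesis of a phase III trial. The same data could give a different estimate, or one of opposite sign, according to the coding. The trial is open-label (11.4), so this choice should not be left until outcome data can be seen.

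BV timing adds to the problem. If the BV term is BV at the test-of-cure visit, the model conditions on something measured after randomisation that treatment may have changed.

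**Working it through.** **1. The plan's own figure.** Inputs from 11.7: p1 = 0.162, p2 = 0.107, power 0.80. The 0.05 level is from 11.13; its sidedness is not stated. With mean rate 0.1345,

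n per arm = [1.960 × √(2 × 0.1345 × 0.8655) + 0.842 × √(0.162 × 0.838 + 0.107 × 0.893)]² / 0.055² = (1.3505 / 0.055)² = 602.9, so 603 per arm and 1206 in total.

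This matches the plan. One-sided 0.05 would give 475 per arm (950), so 1206 implies a two-sided test. No BV term enters: the trial is sized on the overall comparison. At the 1332 evaluable women in 11.7 (666 per arm), the same formula gives 83.8% power, ignoring clustering.

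**2. What the model coefficient is.** Write the model as logit(p) = β0 + β1·T + β2·B + β3·T·B. The arm log odds ratio at BV value b is β1 + β3·b, so β1 is the effect at b = 0:
- 0/1 coding, BV-negative reference: effect in BV-negative women.
- 0/1 coding, BV-positive reference: effect in BV-positive women.
- -1/+1 coding: unweighted mean of the two log odds ratios.

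**3. The protocol's own data.** Table 4 (2.2 Rationale), test-of-cure counts, 7-day v single dose:

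| Quantity | Counts | Odds ratio |
|---|---|---|
| Overall | 9/115 v 21/115 | (9/106)/(21/94) = 0.38 |
| Model, BV-negative reference | 3/40 v 2/35 | (3/37)/(2/33) = 1.34 |
| Model, BV-positive reference | 6/75 v 19/80 | (6/69)/(19/61) = 0.28 |
| Model, -1/+1 coding | both strata | √(1.34 × 0.28) = 0.61 |

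No coding in the table returns the overall value, and the direction reverses with the reference level. This step needs no assumption about BV prevalence.

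**4. Power if the effect is the same in both BV groups.** Take 16.2% v 10.7% in each stratum. The log odds ratio is ln[(0.107/0.893)/(0.162/0.838)] = -0.478. Let u = 1/(0.162 × 0.838) + 1/(0.107 × 0.893) = 17.83 and let q be the BV share. The coefficient's variance is u/[666(1-q)] with BV-negative reference, u/[666q] with BV-positive reference, and one quarter of their sum with -1/+1 coding. Two-sided Wald power at 0.05:

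| BV share | BV-negative ref. | BV-positive ref. | -1/+1 |
|---|---|---|---|
| 29% | 69% | 35% | 76% |
| 44% | 59% | 49% | 83% |
| 61% | 45% | 63% | 81% |
| 67% | 39% | 67% | 78% |

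Simulation (100,000 trials per scenario) agrees within about a point: 70% falling to 39%, 35-67%, and 76-83%. The BV shares are from section 2.2. The 61% and 67% (155/230) come from HIV-positive women with TV. The 29% and 44% come from women not selected for TV. None is for HIV-negative, TV-positive women, so this is an assumed range.

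**5. If H2 is true.** The effect in BV-negative women is then nil, and with that reference β1 = 0. The test rejects at its nominal size: 5% two-sided, of which 2.2-2.5% favours the 7-day arm in simulation.

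**6. Visit for BV.** Section 2.2 frames the hypothesis by the vaginal environment when TV is treated, and plans BV measurement at every visit. It also says that the 7-day regimen is first-line therapy for BV. BV at test of cure is therefore post-randomisation and plausibly changed by arm; baseline BV is neither.

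**7. The stratification rule.** Suppose it were triggered by arm-by-BV at p < 0.10, with unadjusted tests in each stratum, and the overall test used otherwise. With a common rate of 13.45% in every cell (no effect anywhere), two-sided false claims are about 9.4% (9.3-9.5% over the BV shares), against 5% for the overall test alone.

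**The case against.** The strongest reply is that H1 is already identified. Section 11.3 states the overall comparison, H1 is worded as an overall comparison throughout, and 11.7 sizes it so. That stands against any claim that the plan contains no H1 comparison. It does not remove the conflict: 11.3 names no test or level, and 11.13 says that a different analysis is primary and answers H1.

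Four stronger readings are tempting, and the documents do not support them.
- **Power for H1 is about 2%.** That figure is one tail of the test size when the coefficient targets an effect that H2 sets to zero. It shows a wrong target, not lost power, and only under a coding that the plan does not state.
- **Every coding loses power.** If the effect is homogeneous, centring BV at its mean keeps 84%. If H2 is true, the BV-positive reference has about 90% or more.
- **The stratification rule nearly doubles false claims.** The rule follows a discussion of three-way interaction and speaks of an interaction not expected, whereas H2 expects arm-by-BV. It also provides for assessing any remaining interaction within BV strata, which arm-by-BV cannot be. It most naturally concerns a three-way or other interaction, though this is not explicit.
- **BV is undefined.** The cut-point is defined; only coding, reference level and visit are missing.

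The analysis set also needs attention, given the withdrawals and discarded swabs in 8.2, 8.5 and 9.10, but that is a separate matter.

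**Conclusion.** The point holds. As written, 11.13 answers H1 from a model whose treatment coefficient is in general not the comparison described in 11.3 and sized in 11.7. Which quantity it does estimate is left to an unstated coding. The reversal on the Table 4 counts (0.38 overall; 1.34, 0.28 or 0.61 from the model) is plain arithmetic. The power figures (84% against a low of 35-39% for the least favourable codings and BV shares, if the effect is homogeneous) rest on 666 evaluable women per arm, no clustering adjustment and a BV share of 29-67%. The 9.4% false-claim rate is conditional on the less natural reading of the stratification rule and should not be quoted without that condition. The unnamed BV visit is a real second gap, because one permitted choice conditions on a post-randomisation variable; its effect is not quantified here.

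**What to change.** In 11.13:
- Name the overall arm comparison of TV-positive status at test of cure as the H1 test: two-sided 0.05, no BV-by-arm term, done whatever the interaction shows, with a reference to 11.3.
- Optionally add, as supportive, a risk difference from the model standardised over baseline BV. In simulation its power is 84-86% if H2 is true and 84% if the effect is homogeneous, with 5.0-5.1% false positives.
- Use the interaction model for H2 through its interaction term, with stratum estimates and confidence intervals.
- Define its BV term as the baseline Nugent category (7 or more) and state the coding and reference level.
- Say which interaction the p < 0.10 rule concerns, and that stratifying does not replace the H1 test.

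The cost is wording only: no change to sample size, visits or data collected.

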**Table 2. T. vaginalis results by Metronidazole Treatment Arm at Test-of-Cure (n=255) and 3 month (n=152)**

	TV+ Rate Overall % (n)	7 day dose % (n)	Single dose % (n)	RR (95% CI)	P-value
TOC	12.5% (32/255)	8.5% (11/130)	16.8% (21/125)	0.50 (0.25, 1.00)	0.045
3 month	17.8% (27/152)	11.0% (8/73)	24.1% (19/79)	0.46 (0.21, 0.98)	0.030

RR=Relative Risk; CI=Confidence Interval;

representative sample (where the prevalence was 3.1 times greater for African-American women compared to whites), 44% in a group of women at high-risk for HIV, and as high as 56% among injection drug users. Like TV, BV can also increase a woman's susceptibility to HIV infection. Several studies have shown a strong association between TV and BV, meaning that the two frequently occur as co-infections among women. While these two vaginal infections have similar

symptomatology and are treated with similar medication, the dosing is not the same. The Centers for Disease Control and Prevention (CDC) guidelines for treatment of TV include: MTZ or TDZ 2 g single dose as the recommended regimens, and MTZ 500 mg BID 7 day dose as the alternative treatment regimen. For BV, the first line of therapy is 500 mg MTZ BID for 7 days. Thus, the first line of therapy for TV would not adequately treat concomitant BV.

**Table 3. Distribution of *T. vaginalis* according to Nugent Score categories and association between vaginal flora and *T. vaginalis* infections among HIV-positive women (n=356)**

Vaginal Flora (Nugent score)	Number of Women	Percentage infected with T.vaginalis	Odds ratio for T. vaginalis infection	95% confidence interval	P-value
Normal (0-3)	128	16.4%	Ref.	--	--
Intermediate (4-6)	50	40.0%	3.40	1.63, 7.08	0.0008
Bacterial vaginosis (7-10)	187	34.2%	2.65	1.52, 4.63	0.0005
Abnormal (4-10)	237	35.4%	2.80	1.63, 4.79	0.0001

In a screening study of HIV-positive women, we found that the prevalence of TV was higher among women who had altered vaginal flora (Table 3) and that the majority (61.0%) of HIV+/TV+ women also had BV. This high rate of BV that accompanies TV infection among HIV+ women has implications for treatment decisions.

[figure not shown]

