**Table 4. Repeat infection rates at TOC by arm and BV status**

	Percentage overall repeat infection rate TV+ (n)	Percentage baseline coinfection TV/bacterial vaginosis	Percentage baseline single infection TV	RR (95% CI)	p Value
Test-of-cure (N=230)	13.0 (30/230)	16.1 (25/155)	6.7 (5/75)	2.42 (0.96 to 6.07)	0.05
Single-dose	18.3 (21/115)	23.8 (19/80)	5.7 (2/35)	4.16 (1.02 to 16.89)	0.02
7-day dose	7.8 (9/115)	8.0 (6/75)	7.5 (3/40)	1.07 (0.28 to 4.04)	0.92
3 month (N=138)	16.7 (23/138)	19.1 (16/84)	13.0 (7/54)	1.47 (0.65 to 3.34)	0.35
Single-dose	22.2 (16/72)	25.6 (11/43)	17.2 (5/29)	1.48 (0.58 to 3.82)	0.40
7-day dose	10.6 (7/66)	12.2 (5/41)	8.0 (2/25)	1.52 (0.32 to 7.27)	0.70 Fisher exact test

These data suggest that the vaginal environment associated with BV at the time of TV treatment in some way partially protects the organism (TV) from the effects of single-dose MTZ but over a more prolonged period of time the effect is largely lost. The influence of the vaginal environment on TV treatment has been alluded to in other studies. Over 40 years ago, Nicol et al. reported the possibility that inactivation of MTZ might be the cause of multiple treatment failures in a woman infected with a TV strain that was susceptible to the drug in vitro. A few years later, McFadzean et al. described inactivation of MTZ by bacteria isolated from 16 samples taken from 84 women with TV vaginitis. Ten of the organisms were Gram-positive cocci including 7 cases of *Streptococcus (Enterococcus) faecalis*. The six others were Gram negative rods including *Escherichia coli*, *Proteus* spp. and *Klebsiella* spp. More recently, several papers have reported that various members of the genus *Enterococcus* are capable of inactivating MTZ. Deep sequencing studies have not found many of these organisms in patients with BV but it could be that even minor populations of certain organisms or combinations of organisms may have the ability to inactivate MTZ clinically.

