## **11.5 Appropriate Methods and Timing for Analyzing Outcome Measures.**

The primary outcome measure is TV infection. All women will be TV positive at baseline and will be screened for TV using InPouch culture and NAAT at follow up visits. Binary (TV positive or TV negative)

Key secondary outcomes are:

Version: 11.0

Version date: 1/2/17

BV which will be measured by self-collected vaginal swabs and Gram stain screening at all visits. Categorical (Scores of 7 -10 are considered to indicate BV). This measure will add information about the primary outcome measure by indicating whether BV affects TV repeat infections.

Re-exposure, which will be self-report by the participant for each partner. This data will be collected on the behavioral survey at follow up visits. Binary (partner treated and /or no sexual exposure prior to screening vs. partner not treated and sexual exposure prior to screening, This measure will allow us to adjust for the confounding effects of sexual exposure/re-exposure.

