## 11.6 Study Hypotheses

From the two aims, there are two hypotheses:

H1: Multi-dose (alternate) MTZ is superior to the single dose (recommended) for the treatment of TV among HIV-negative women.

H2: Altered vaginal flora (measured by Nugent's score) interferes with the MTZ treatment of TV for the single dose but not the multi-dose.

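### The BV term in the primary model is not fixed to baseline and reads most naturally as BV at test of cure, which is measured after treatment and does not test H2

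*Combined protocol and SAP*

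**What the plan says.** Section 11.13 answers H1 and H2 with one logistic model for repeat TV infection. It contains dose, BV and their product, and the BV term is defined as "Factor 2) BV at time of visit". The outcome is TV at the TOC visit (section 4.2.1).

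Section 11.5 lists, among the key secondary outcomes, "BV which will be measured by self-collected vaginal swabs and Gram stain screening at all visits", so each evaluable woman should have at least a baseline and a TOC value. Section 11.3 says "Additional analyses will be conducted to compare the rates stratified by BV status", and section 11.13 also stratifies on BV status if the interaction is significant or near-significant. Neither names a visit.

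H2, as stated in the summary and in sections 3.1, 11.7 and 11.13, refers to women with a Nugent score of 7 or more and gives no time point. Section 11.6 words it as altered flora that "interferes with the MTZ treatment of TV for the single dose but not the multi-dose". The rationale (section 2.2) attributes the effect to "the vaginal environment associated with BV at the time of TV treatment", and the relevant column of Table 4 is headed "Percentage baseline coinfection TV/bacterial vaginosis".

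On the drug's effect on BV itself, section 2.2 says "For BV, the first line of therapy is 500 mg MTZ BID for 7 days" and that "the first line of therapy for TV would not adequately treat concomitant BV".

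**The concern.** H2 is one of two primary hypotheses, and this term defines its test. If BV is taken at TOC, women are grouped by something that happened after randomization and that the assigned dose is expected to change. The group without BV at TOC then mixes women who never had BV with women whose BV cleared, in proportions that differ by arm. Three things can follow:

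- A true H2 can be diluted, with an apparent 7-day benefit in women labelled BV-negative.
- A false H2 can appear true, because unequal clearance alone produces an interaction.
- The same model serves H1. With 0/1 coding and the interaction included, the dose coefficient applies only to women without BV, so under the TOC reading the H1 estimate also rests on a group formed after treatment.

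If the authors meant baseline, the text still does not say so. The trial is unblinded (section 11.4), and an unnamed visit leaves the choice open until results are known.

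**Working it through.** **The plan's own figures.** With 16.2% versus 10.7%, two-sided 5% and 80% power, without continuity correction: n per arm = (1.96 × √0.2328 + 0.8416 × √0.2313)² / 0.055² = 603, so 1206 in total. Then 1206 × 1.15 × 1.20 = 1664. Section 11.7 expects 1332 evaluable, or 666 per arm. The BV term plays no part in this, so the fix leaves N alone.

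**Method.** Let b be the share with baseline BV, c the clearance in an arm, r the share of baseline BV-negative women with new BV at TOC, and p₁, p₀ the TV rates with and without baseline BV. TOC BV is taken as independent of TV given baseline BV and arm.

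- Share with BV at TOC: b(1−c) + (1−b)r
- TV rate among them: [b(1−c)p₁ + (1−b)r·p₀] / that share
- TV rate without BV at TOC: [b·c·p₁ + (1−b)(1−r)p₀] / (1 − that share)
- SE of the log ratio of odds ratios: square root of the sum over the four cells of 1/[666·w·p(1−p)], where w is the cell's share of its arm
- Power: two-sided 5% Wald test, no clustering

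**Assumptions.** Single-dose clearance is 10–50% and 7-day clearance 30–80% in steps of 10, with 7-day not below single (27 pairs), and r = 10%. None of these is in the documents. There are three truths:

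- (a) H2 true: b = 60%; TV 8% in both arms without BV; 21.7% single and 12.5% 7-day with BV. These BV-specific rates are assumed, but they return the planning marginals: 0.6 × 21.67 + 0.4 × 8 = 16.2 and 0.6 × 12.5 + 0.4 × 8 = 10.7.
- (b) Table 4 rates: 19/80 and 2/35 for single dose, 6/75 and 3/40 for 7-day, b = 155/230 = 67%.
- (c) H2 false: the single-dose rates and b of (a), with an odds ratio of 0.62 in both baseline-BV groups.

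**Worked case: truth (a), clearance 40% single and 70% 7-day.**

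- Single dose: TOC-BV share 0.6 × 0.6 + 0.4 × 0.1 = 0.40. TV with BV (0.36 × 0.2167 + 0.04 × 0.08)/0.40 = 20.3%. TV without BV (0.24 × 0.2167 + 0.36 × 0.08)/0.60 = 13.5%.
- 7-day: TOC-BV share 0.6 × 0.3 + 0.04 = 0.22. TV with BV (0.18 × 0.125 + 0.04 × 0.08)/0.22 = 11.7%. TV without BV (0.42 × 0.125 + 0.36 × 0.08)/0.78 = 10.4%.
- Odds ratios, 7-day versus single: 0.52 with BV and 0.75 without, ratio 0.69. SE is 0.362, so z is about 1.0 and power 17%.
- With baseline BV: odds ratios 0.52 and 1.00, ratio 0.52. SE is 0.374, so z is about 1.77 and power 42%.

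**Whole grid** (clearance pairs are single/7-day, %).

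| Truth | Quantity | Baseline BV | TOC BV, range | 40/70 | 40/40 | 10/50 |
|---|---|---|---|---|---|---|
| (a) | Ratio of ORs | 0.52 | 0.46–0.80 | 0.69 | 0.77 | 0.51 |
| (a) | OR, no BV | 1.00 | 0.67–1.07 | 0.75 | 0.70 | 1.01 |
| (a) | Interaction power | 42% | 10–49% | 17% | 12% | 47% |
| (b) | Ratio of ORs | 0.21 | 0.34–0.65 | | | |
| (b) | OR, no BV | 1.34 | 0.46–0.85 | | | |
| (b) | Interaction power | 94% | 17–78% | | | |
| (c) | Ratio of ORs | 1.00 | 0.50–0.92 (24 unequal pairs) | 0.79 | 0.99 | 0.63 |
| (c) | False rejection | 5% | 6–41% (24 unequal pairs) | 10% | 5% | 26% |

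In (a) the ratio moves toward 1 in 23 of 27 pairs; in (b) it does so in all 27. Simulation with 20,000 trials per case agrees. For (a) it gives 43% with baseline BV and 17%, 12% and 48% for 40/70, 40/40 and 10/50. For (c) it gives 5% with baseline BV and 9%, 5% and 27%.

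**Relaxing the fixed inputs.** A separate calculation on the Table 4 rates used 50–90% persistence after single dose, 20–50% after 7 days and 0–20% new BV, with and without doubled odds of BV at TOC when TV persists. The ratio was 0.38–0.65, the odds ratio without BV 0.46–0.89 and power 22–71%.

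**The case against.** The strongest reply is that the authors meant baseline. The exclusion criteria (section 5.1.2) speak of BV treatment at visit when they mean the enrolment clinic visit. Study drug is given only at baseline (section 9.6). Table 4 splits by baseline coinfection. Section 2.2 gives follow-up BV a purpose of its own, comparing women whose BV resolved with those whose BV did not. On that view the defect is an unnamed visit, and the distortions describe an analysis nobody planned. The competing reading is real, and the TOC reading is not certain. But no passage settles it, and a plan followed literally, with TV at TOC as the outcome, leads to BV at TOC.

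It is also fair that H2 as written carries no time point. That it concerns BV at treatment is inferred from sections 2.2 and 11.6.

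The H1 objection stands in part. The dose coefficient refers to women without BV whichever visit is used, so naming the visit does not cure that, and section 11.3 already describes a direct comparison of arms. What the TOC reading adds is that this reference group is itself formed after randomization.

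Section 11.5 gives BV an explanatory role as well as listing it as an outcome, so the list alone does not show it is purely an outcome. The argument rests on the expected effect of dose on BV instead.

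On size, the inputs are largely assumed, the Table 4 cells are small and come from HIV-positive women, and the results run from no distortion to a large one. All of that is correct. It limits what can be said about direction and amount, but does not make the term suitable for H2.

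**Conclusion.** The concern holds. As written, the BV term for a primary hypothesis is either post-treatment, on the natural reading, or undefined, and neither gives a clear test of H2. The harm is not fixed in direction. If H2 is true at the planning rates, power goes from 42% to between 10% and 49%, usually downward. With Table 4 rates it falls from about 94% to between 17% and 78%. If H2 is false, unequal clearance raises the rejection rate from 5% to between 6% and 41%, while equal clearance leaves it at 5%. At 10/50 clearance with H2 true there is essentially no distortion.

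These figures depend on assumed BV clearance, on assumed TV rates by BV status in (a) and (c), on HIV-positive pilot data in (b), and on ignoring clustering by site. The qualitative conclusion needs only the protocol's statements that the 7-day regimen is first-line treatment for BV and that first-line TV therapy does not adequately treat it. This should be corrected before the data are analysed.

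**What to change.** In section 11.13, define Factor 2 as Nugent score 7 or more on the swab taken before randomization, and use the same definition for the BV strata in sections 11.3 and 11.13. Estimate H1 without any post-treatment BV term, as the direct arm comparison in section 11.3 allows. Analyse BV at TOC by arm as a secondary outcome. Label the comparison of resolved with unresolved BV (section 2.2) as exploratory and non-randomized.

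The cost is about one line in the analysis plan. The baseline Gram stain is already collected before randomization (sections 8.2 and 11.4), and neither the sample size nor the visit schedule changes.
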